Modest activity is considered clinically meaningful in this relatively heavily pretreated population with metastatic CRPC that has received abiraterone acetate and/or enzalutamide (prior chemotherapy and sipuleucel-T are allowed). The null hypothesis for this trial is that the primary endpoint of 6-month PFS <10% is not clinically meaningful and the alternative hypothesis is that the true clinical PFS of interest is $\geq 30\%$. Since we will follow all subjects for at least 6 months or until progression or death, we will not have censoring and 6 months PFS can be treated as a binomial random variable. With twenty five evaluable patients we will have 80% power for an exact binomial test at the one sided 0.05 significance level of the null hypothesis that the 6-month PFS rate is 10% if the actual rate is 30%. That null hypothesis will be rejected if 6 or more of the 25 subjects survive for 6 months progression free. Twenty-eight subjects will be accrued to allow for 10% inevaluable patients.

Sample Size/Accrual Rate

A total of 28 patients will be enrolled for this trial. Accrual period will be 6 to 12 months.

Analysis of Secondary Endpoints

The Kaplan-Meier method will be used to estimate PFS and OS rates over time with standard errors estimated using Greenwood's formula. Medians and their 95% confidence intervals will also be estimated. PSA response, PSA decline $\geq 30\%$ within 3 months, RECIST responses and regressions, pain response and CTC alterations will be analyzed as secondary endpoints. CTC changes will include changes from unfavorable ($\leq 5/7.5\text{ml}$) to favorable, and declines by $>30\%$. Pain response is defined as decline in present pain index ≥ 2 points and/or decrease in analgesics. Linear regression with PSA as the dependent variable and time as the dependent variable will be performed and used to estimate PSA DT. The association of baseline whole blood 20S proteasome level with PFS and other secondary endpoints will be examined using Cox regression to generate hypotheses for selecting suitable patients for further study.

Reporting and Exclusions

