Pain response and progression

Patients with a PPI score of at least 2, or need for analgesics, or both at baseline are assessed for the pain response. A pain response is defined as a two-point reduction in the PPI score from baseline without an increase in the analgesic use or as a reduction in analgesic use without an increase in the PPI score. Pain progression is defined as an increase in the PPI score of at least one point from the nadir, an increase in analgesic use, or a requirement for palliative radiotherapy.

Progression-Free Survival

PFS is defined as the duration of time from start of treatment to time of progression or death, whichever comes first.

12. **CORRELATIVE STUDIES**

Circulating Tumor Cell (CTC) enumeration will be used as a secondary marker for efficacy of response to the treatment. Baseline CTC will be obtained prior to initiation of therapy and day 1 of cycles 2 and 4. Baseline whole blood 20S proteasome activity will also be determined.

CTC enumeration

The CELLSEARCH[®] System led to the first standardized, FDA-cleared semi-automated system that detects and enumerates CTCs of epithelial origin (CD45-, EpCAM+, and cytokeratins 8, 18+, and/or 19+) from a 7.5-mL blood sample with high sensitivity and specificity. The CELLSEARCH[®] System uses unique immunomagnetic and fluorescence imaging technology to provide rapid and reproducible analysis of CTCs with a simple 3-step process: sample collection, sample preparation, and sample analysis. System components include:

- Proprietary CellSave Preservative sample tubes
- CELLSEARCH[®] CTC Test and Control kits
- Automated CELLTRACKS[®] AUTOPREP[®] System
- CELLTRACKS ANALYZER II[®]

CellSave Preservative tubes provide an optimized cell preservative that stabilizes CTCs for up to 96 hours at room temperature, which allows shipment of samples to remote locations for analysis and improves the reproducibility and reliability of CTC analysis. CTCs are fragile and tend to degrade within a few hours when collected in standard evacuated blood collection tubes.

Once the blood sample is collected for UAB patients, the tube will be delivered to UAB main laboratory to be sent out to Quest Diagnostics for CTC enumeration. For outside sites, the tube will be sent directly to Quest Diagnostics for CTC enumeration.

Whole Blood 20S Proteasome Activity

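### Sections 10 and 11 define pain response differently, so some patients are responders under Section 10 but non-responders with pain progression under Section 11

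*Combined protocol and SAP*

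**What the plan says.** Section 10 (Analysis of Secondary Endpoints) states: "Pain response is defined as decline in present pain index" of at least 2 points, and/or a decrease in analgesics. It adds no condition, no baseline requirement and no reference to Section 11. The secondary objectives, in the Synopsis and Section 2.2, use the same two components, also without conditions.

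Section 11 (Pain response and progression) gives a second definition. The first limb reads "A pain response is defined as a two-point reduction in the PPI score from baseline without an increase in the analgesic use". The second is "a reduction in analgesic use without an increase in the PPI score". The population is restricted: "Patients with a PPI score of at least 2, or need for analgesics, or both at baseline are assessed for the pain response". The same paragraph says "Pain progression is defined as an increase in the PPI score of at least one point from the nadir, an increase in analgesic use", with need for palliative radiotherapy as a third route. Each route is sufficient alone.

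Worsening of pain is also a component of clinical progression, and its wording varies. The Synopsis and Section 3.1 list a PPI rise of at least 1 point and a greater need for analgesics, separated by a comma with neither 'and' nor 'or'. Sections 6.3 and 10 leave the matter to the investigator's judgment.

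**The concern.** Two sections each claim to define the same endpoint, and they disagree about patients whose two components move in opposite directions. Section 10 is the analysis section, so an analyst could follow it in good faith and count as efficacy responses patients whom Section 11 classes as having pain progression. Another analyst, following Section 11, would report a different numerator and a different denominator from the same data.

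Section 1.4 names pain responses among the supportive evidence for efficacy. In an uncontrolled trial, a fall in pain that coincides with more analgesic use is hard to attribute to study drug, and the Section 11 conditions guard against counting it. The conflicting combinations can be observed: PPI and analgesic intake are recorded on day 1 of every cycle, and Appendix C classes analgesic use as increased, decreased or unchanged.

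**Working it through.** The plan gives no figure for pain response, so there is none to reproduce. The check is a comparison of the rules.

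**Inputs.** PPI takes values 0 to 5 (Appendix B). Analgesic change has three values (Appendix C). The response and progression rules come from Sections 10 and 11. The comparison is made at the first post-baseline assessment, so the nadir is the baseline value. Section 11's two-point reduction is read as at least two points.

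**Enumeration.** 6 baseline scores × 6 current scores × 3 analgesic changes = 108 combinations. Those that count as a response under Section 10 are:

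| Combination | Count | Section 10 response | Section 11 response | Section 11 pain progression |
|---|---|---|---|---|
| PPI down ≥2, analgesics unchanged | 10 | yes | yes | no |
| PPI down ≥2, analgesics decreased | 10 | yes | yes | no |
| PPI down 1 or unchanged, analgesics decreased | 11 | yes | yes | no |
| PPI down ≥2, analgesics increased | 10 | yes | **no** | **yes** |
| PPI up ≥1, analgesics decreased | 15 | yes | **no** | **yes** |

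Total under Section 10: 10 + 10 + 11 + 10 + 15 = 56. Section 11 rejects 10 + 15 = 25 of them, and all 25 are pain progression there. Under the Section 11 response rule, none of the 108 combinations is both a response and a pain progression. These are counts of logical possibilities, not expected patient rates.

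**Weight of one patient.** 1/28 = 3.6 points on those enrolled; 1/25 = 4.0 points on the evaluable number used for the primary test. The number with baseline pain or analgesic need is not stated. If it were 10 to 15 (an assumption), one patient would be 1/15 = 6.7 to 1/10 = 10 points.

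**Direction of the rate.** Measured from baseline, a patient outside the Section 11 population has PPI 0 or 1 and no analgesic need. He can neither fall 2 points nor reduce analgesics, so the Section 11 population leaves out only patients who cannot respond. Suppose, purely for illustration, 28 patients, 10 Section 10 responders and 2 of those discordant. Section 10 over all patients gives 10/28 = 35.7%. Section 11 gives 8/15 = 53.3% if 15 patients are symptomatic, but 8/25 = 32.0% if 25 are. The crossover is at 28 × 8/10 = 22.4 symptomatic patients. With the denominator held at 15, the definitions give 10/15 = 66.7% and 8/15 = 53.3%.

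**Primary design.** Rejecting at 6 or more of 25 gives exact one-sided alpha 0.0334 and power 0.807, consistent with the stated 0.05 level and 80%. 25/0.90 = 27.8, rounded up to 28. None of these uses the pain-response definition.

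**The case against.** The best defence is that Section 10 is shorthand. Section 11 holds the operational rules for measuring effect, and Section 10 also names RECIST response without repeating its criteria. That is plausible, but for RECIST Section 10 offers no competing definition. For pain it supplies one, with no pointer to Section 11 and in the same unconditional form as the objectives.

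It is also fair that the consequence is limited. Pain response is one of several secondary endpoints with no formal test, and the number of discordant patients could be zero.

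Four stronger readings are tempting and are not supported:

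- A reader might infer that Section 10 inflates the reported rate. It enlarges the numerator, but the two sections also imply different denominators, so the net direction depends on data the documents do not give.
- A reader might infer that the Section 10 rule contradicts the primary endpoint. Section 11 does not say that its pain-progression rule is the PFS criterion. The conflict reaches PFS only through the Synopsis and Section 3.1 list, and only if its comma means 'or'; Sections 6.3 and 10 use investigator judgment.
- A reader might say that pain fell only because analgesics were raised. Neither definition tests cause; each uses only the direction of change.
- A reader might say that the pain-response denominator is undefined. Section 10 omits it, but Section 11 states it.

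**Conclusion.** The concern holds as a conflict between two stated definitions. Both kinds of discordant patient are responders in Section 10 and non-responders with pain progression in Section 11, so following Section 10 as written adds them to the response numerator. This is a conflicting rule, not merely missing detail, and it should be settled before the endpoint is analysed.

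The size per patient is 3.6 points on 28 or 4 points on 25, and larger in the symptomatic subset. Neither the number of discordant patients nor the net change in the rate can be derived from the documents. The primary test, its alpha and its power do not change.

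The finding that no combination is both a response and a progression under Section 11 applies to the first post-baseline assessment. Later on, a rise from the nadir can follow a genuine response, which is a separate matter.

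**What to change.** Replace the pain-response sentence in Section 10 with the Section 11 definition, including both conditions and the baseline population, or state in Section 10 that Section 11 governs. Align the short form in the objectives (Synopsis and Section 2.2).

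Separately, reconcile the differing wordings of pain worsening in the Synopsis, Sections 3.1, 6.3 and 10, and the pain-progression rule in Section 11. Say whether the Section 11 rule is meant to be the PFS pain criterion. Because that criterion also ends treatment, which wording to keep is for the investigators to decide.

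The cost is a few sentences and no new data collection. Discordant patients would no longer count as responders, and the rate would be reported on the symptomatic subset.

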The choice of a primary endpoint in metastatic CRPC is difficult as this disease is characterized by a poor ability to measure response and PFS, the typical primary endpoints in phase II trials. Measurable lesions by RECIST are seldom observed, since the most common site of metastases is bone, a non-measurable site [26]. Although, a $\geq 30\%$ or $\geq 50\%$ PSA decline within 3 months and time to clinical progression may be useful surrogates for long-term outcomes with chemotherapeutic agents, its validity with biological agents is unknown [27-29]. Regression of measurable tumor was associated with survival in one study, but external validation is required and measurable tumors are found in the minority of patients. Prostate Cancer Working Group (PCWG)-2 guidelines recommend time to event primary endpoints rather than response endpoints [27]. Moreover, an early switch in therapy within 3 months was discouraged due to the poor reliability of early changes in PSA and bone scans. Vaccines may potentially induce a transient rise in PSA as well as increases in size of measurable lesions by provoking an immune reaction in the normal and malignant prostate tissue. Guidelines have been recommended to standardize methodology used for the calculation and employment of PSA doubling time changes to provide a signal of activity in early trials [30].

Changes in CTCs (circulating tumor cells) appear promising as prognostic factors in the setting of chemotherapy and abiraterone, but require validation in the context of biologic agents [31, 32]. Moreover, it is unclear if unfavorable CTC alterations can be utilized to switch therapy. CTC is emerging as a highly important prognostic marker for metastatic CRPC and appears better than PSA. In one prospective trial, blood was drawn from CRPC patients with progressive disease starting a new line of chemotherapy before

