2.2 Secondary Objectives

- PSA changes (response, PSA decline $\geq 30\%$ within 3 months)
- CTC changes (unfavorable \rightarrow favorable, $>30\%$ decline)
- Measurable disease response rate (RECIST)
- Pain responses (decline in present pain index ≥ 2 , decrease in analgesics)
- Overall Survival

- Toxicities
- Association of outcomes with baseline whole blood 20S proteasome level

[figure not shown]

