3.2 Trial schema

4. PATIENT SELECTION

4.1 Eligibility Criteria

Each patient must meet all of the following inclusion criteria to be enrolled in the study:

1. Histologically proven adenocarcinoma of the prostate
2. Metastatic disease
3. Progressive disease (PSA, radiologic, symptomatic) following abiraterone acetate and/or enzalutamide (prior chemotherapy and sipuleucel-T is allowed); PSA progression is defined as baseline increase followed by any PSA increase ≥ 1 week apart
4. Voluntary written informed consent before performance of any study-related procedure not part of normal medical care, with the understanding that consent may be withdrawn by the subject at any time without prejudice to future medical care.
5. Patients, even if surgically sterilized (i.e., status post-vasectomy) must agree to 1 of the following: practice effective barrier contraception during the entire study treatment period and through a minimum of 30 days after the last dose of study drug, or completely abstain from heterosexual intercourse if female partner of childbearing age.
6. An elevated PSA level of >2 ng/mL for patients progressing by PSA criteria is required (last confirmatory sample must be >2 ng/mL)
7. Currently on androgen ablation hormone therapy (an LHRH agonist/antagonist or orchiectomy) with testosterone level <50 ng/dL)
8. Has an ECOG Performance Status (PS) of 0-2 (Appendix A)
9. LVEF $\geq 40\%$ on 2-D transthoracic echocardiogram (ECHO); Multigated Acquisition Scan (MUGA) is acceptable.
10. Is ≥ 19 years of age
11. Resolution of all acute toxic effects of prior chemotherapy or surgical procedures to NCI CTCAE Version 4.03 Grade <1 , in the opinion of the Treating Physician (Appendix D)
12. Ability to understand and the willingness to sign a written informed consent document.

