8. STUDY CALENDAR

Baseline evaluations are to be conducted within 2 weeks prior to administration of protocol therapy. Scans and x-rays must be done ≤4 weeks prior to the start of therapy. In the event that the patient's condition is deteriorating, laboratory evaluations should be repeated within 48 hours prior to initiation of the next cycle of therapy.

	-28 days	-14 days (may serve as cycle 1 day 1 labs)	Day 1 (± 1 day) of every cycle (28 days)	Day 8 and 15 every cycle (± 1 day)	Day 1 Every 3 cycles	30 (± 7 days) post last treatment
ASSESSMENTS						
History and exam (H&P)	X		X			X ¹
ECOG performance status		X	X			X ¹
CBC with differential		X	X	X		X ¹
CMP		X	X			X ¹
PSA		X	X			X ¹
LDH		X				
Testosterone level		X				
Pain (PPI 0-5 scale)		X	X			X ¹
Analgesic intake (increased, decreased or stable)		X	X			X ¹
Echocardiogram	X		X ^{6,7}			
DISEASE ASSESSMENT						

CT chest , abdomen, pelvis	X				X	X ¹
Bone Scan	X				X	X ¹
TREATMENT						
Carfilzomib day 1,2, 8,9,15,16 (30 min IV infusion)			X ²	X ²		
Premedication (Dexamethasone, Acetaminophen)			X ³	X ³		
Pre-hydration (Normal saline 250-500 ml over 30 minutes)			X ⁴	X ⁴		
Acyclovir 400 mg PO bid			X ⁵	X ⁵		
LHRH analogue (if no prior orchiectomy)					X	
CORRELATIVE STUDIES						
CTC enumeration (3 time points)	X		X (cycle 2 only)		X (cycle 4 only)	
Whole Blood 20S proteasome assay	X					
FOLLOW-UP						
Disease progression and survival						X ¹

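### The PSA doubling-time sentence regresses untransformed PSA, calls time a dependent variable and gives no conversion formula, so followed literally it does not yield a doubling time

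*Combined protocol and SAP*

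**What the plan says.** The method is one sentence in Section 10, under Analysis of Secondary Endpoints: "Linear regression with PSA as the dependent variable and time as the dependent variable will be performed and used to estimate PSA DT". No log or other transformation is mentioned. No formula links the regression output to a doubling time. There is no observation window, no minimum number of values, and no rule for a flat or falling PSA.

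The only other mention of doubling time is a background remark in Section 1.1: "Guidelines have been recommended to standardize methodology used for the calculation and employment of PSA doubling time changes". It contains no formula, and Section 10 does not refer to it.

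Three other places bear on the point:

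- **Sampling.** The study calendar (Section 8) places PSA at baseline, then on "Day 1 (± 1 day) of every cycle (28 days"), and after treatment ends.
- **Range of PSA at entry.** Section 4.1 sets only a floor: "An elevated PSA level of >2 ng/mL for patients progressing by PSA criteria is required". There is no ceiling.
- **Status of the measure.** The PSA item in Section 2.2 begins "PSA changes (response, PSA decline" and goes on to the 30% threshold. Doubling time is not among the objectives.

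**The concern.** A quantity has a constant doubling time only if it grows exponentially, that is, if its logarithm is linear in time. The doubling time is then ln(2) divided by the slope of ln(PSA) on time. The slope of untransformed PSA is in ng/mL per month. It is an absolute rate of rise, not a growth rate.

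An analyst who follows the sentence as written must therefore invent a conversion. Different conversions give different answers, and none of those obvious from a raw-PSA fit reliably recovers the doubling time. The values could be reported as a measure of tumour kinetics. They could also enter the exploratory Cox work on baseline 20S proteasome activity, if doubling time is counted among the other secondary endpoints named there.

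**Working it through.** The plan states no numerical doubling time, so there is no figure to reproduce. The check applies the stated regression to PSA series whose doubling time is known.

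**Assumptions.** PSA follows P0 × 2^(t/DT) without noise. The true DT (mainly 3 months) and the starting levels P0 are illustrative and do not come from the documents. Visit spacing is either monthly or the protocol's 28 days (28/30.4375 = 0.920 months).

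**1. A straight line has no constant doubling time.** For a fitted line a + bt, the time to double from time s is (a + bs)/b = a/b + s. It lengthens by one month for every month that passes.

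**2. Conversion A: ln(2) divided by the raw slope.** Use DT = 3, P0 = 10 and 7 monthly values (t = 0 to 6): 10, 12.60, 15.87, 20, 25.20, 31.75, 40.

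- Slope b = Σ(t − 3)y / Σ(t − 3)² = 137.62/28 = 4.915 ng/mL per month.
- Mean PSA = 155.42/7 = 22.203, so intercept a = 22.203 − 3 × 4.915 = 7.458.
- ln(2)/b = 0.693/4.915 = 0.141 months.

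With P0 = 100 every value is 10 times larger, so b = 49.15 and ln(2)/b = 0.0141 months. Growth is identical, the results differ 10-fold, and neither is near 3. On the 28-day schedule with 4 visits, starting levels of 5, 20, 50 and 200 ng/mL give 0.430, 0.107, 0.043 and 0.011 months, a 40-fold spread.

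**3. Conversion B: fitted intercept divided by slope.** This is the time for the fitted line to double from its value at time zero. Both a and b are proportional to P0, so the level cancels: 7.458/4.915 = 74.58/49.15 = 1.517 months for either starting PSA above. The result now depends on the length of observation. For P0 = 20 and DT = 3 on the 28-day schedule:

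- 4 visits: a = 19.39, b = 6.455, a/b = 3.00.
- 7 visits: a = 15.93, b = 9.212, a/b = 1.73.

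The 3.00 is a coincidence of that window, as other doubling times show:

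| True DT (months) | a/b, 4 visits | a/b, 7 visits | ln(2)/slope of ln(PSA), either |
|---|---|---|---|
| 2 | 1.59 | 0.36 | 2.00 |
| 3 | 3.00 | 1.73 | 3.00 |
| 6 | 7.30 | 5.98 | 6.00 |

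**4. Log regression.** Because ln(PSA) = ln(P0) + t × ln(2)/DT, the slope is ln(2)/DT and ln(2)/slope = DT. This holds exactly at every level and for every window in these noise-free series.

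**The case against.** The strongest reply is that this is a dropped word. Calling both variables dependent shows the sentence was not proofread, and a competent analyst would take logs anyway. That may well be what happened. But nothing elsewhere in the documents supplies the log or the formula, and a sentence that is also wrong about time is a poor guide to intent.

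A second reply is that the measure hardly matters. Doubling time is absent from the objectives, from the synopsis statistics and from Section 10's own enumeration of secondary endpoints. It feeds no test, decision rule or progression definition. All of that stands, and it limits the weight of the point.

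A reader might go further than the documents allow in three ways:

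- **That equal growth at different PSA levels must give different values, or that patients would be ranked by PSA burden.** This holds for the raw slope and for conversion A only. Under conversion B the level cancels and, on a common visit schedule, the order of the true doubling times is kept (see the table). The plan names neither conversion.
- **That the distortion, by tracking time on study, biases the trial's result.** Length of observation matters under both conversions, and patients may differ in it. But the primary analysis makes no use of doubling time, and PSA progression alone is not a progression event.
- **That Section 1.1 contradicts Section 10.** It only notes that guidance exists.

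Finally, the exactness of log regression is shown here on ideal data. A PSA that falls and then rises is not log-linear, and one slope over all values would describe it badly. That is a reason to define the window.

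**Conclusion.** The point holds. As written, the sentence omits the log, mislabels time and gives no conversion, so it does not define a doubling time. The size of the error depends on the conversion chosen. With a true value of 3 months, ln(2)/raw slope is far too small and inversely proportional to PSA level, whereas intercept/slope moves between 3.00 and 1.73 months as the visits go from 4 to 7. These figures rest on assumed doubling times and starting levels and on noise-free exponential growth. The algebra behind them does not depend on the particular values chosen.

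The consequence is limited to an unlisted descriptive measure and any exploratory use made of it. The sample size, the primary test and its rejection rule are unaffected. The sentence should be corrected before the analysis, but it is no threat to the trial's main conclusion.

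**What to change.** Replace the sentence in Section 10 with:

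> For each patient, ln(PSA) (dependent variable) will be regressed on time in months (independent variable); PSA DT = ln(2)/slope; patients with a slope of zero or below are reported as not doubling.

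Add a line stating which PSA values enter the regression (the window, including whether baseline and post-treatment values count) and the minimum number of values a patient needs. If doubling time is meant to be a secondary endpoint, list it in Section 2.2; otherwise label it exploratory.

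The cost is two or three lines of text. The PSA values already scheduled are sufficient, and no visit, assay or sample-size change follows.

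### Cox regression is prescribed for relating the 20S level to every secondary endpoint, but as the plan defines them only PFS and OS are time-to-event outcomes

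*Combined protocol and SAP*

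**What the plan says.** Section 2.2 lists as its last secondary objective "Association of outcomes with baseline whole blood 20S proteasome level". The method is one sentence in Section 10 (Analysis of Secondary Endpoints), repeated in the Synopsis: "The association of baseline whole blood 20S proteasome level with PFS and other secondary endpoints will be examined using Cox regression to generate hypotheses". The stated purpose is to help choose suitable patients for further study. No logistic, exact or rank-based method is named for this objective.

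The plan describes the endpoints as follows.

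- **PFS and OS.** Section 10: "The Kaplan-Meier method will be used to estimate PFS and OS rates over time". Section 11 gives PFS an origin and an end: "PFS is defined as the duration of time from start of treatment to time of progression or death, whichever comes first".
- **PSA.** Response, and a decline of at least 30% within a 3-month window (Sections 2.2 and 10).
- **RECIST, pain and CTC.** Section 10: "RECIST responses and regressions, pain response and CTC alterations will be analyzed as secondary endpoints". Section 2.2 words the RECIST objective as a rate.
- **Pain.** Section 11: "A pain response is defined as a two-point reduction in the PPI score from baseline without an increase in the analgesic use", or less analgesic use without a higher score.
- **CTC.** Section 12: "Baseline CTC will be obtained prior to initiation of therapy and day 1 of cycles 2 and 4". The outcome is conversion from unfavorable to favorable, or a decline of more than 30%.
- **Toxicity.** Graded by CTCAE 4.03 (Section 10, Reporting and Exclusions).

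**The concern.** A Cox model cannot be fitted to a responder status until someone decides when the clock starts, what date counts as the event, and when and why a non-responder is censored. The plan decides none of these for the PSA, RECIST, pain, CTC or toxicity outcomes. The choices would be made at analysis, in 25 to 28 patients, and they are not equivalent.

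The 20S level is the candidate marker that Section 1.2 puts forward, while noting that no such marker has been clinically validated. If the clock is chosen badly, a marker that is merely prognostic for progression could be reported as associated with response, and a later trial might select patients on that basis.

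**Working it through.** **1. The plan's own figures.** The plan gives no figure for the 20S analysis. Its primary design reproduces: rejecting at 6 or more of 25, P(X ≥ 6 | 0.10) = 0.033 and P(X ≥ 6 | 0.30) = 0.807, against the stated one-sided 0.05 and 80%. Also 25 / (1 − 0.10) = 27.8, which rounds up to 28. Nothing below changes these.

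**2. Endpoint against model.** Section 2.2 has six secondary bullets apart from the association itself.

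| Objective | Form in the plan | Origin, event date and censoring rule? | Fits Cox as written? |
|---|---|---|---|
| PSA changes | status, one part in a 3-month window | no | no |
| CTC changes | status at two later draws | no | no |
| RECIST response | rate | no | no |
| Pain response | change from baseline | no | no |
| Overall survival | Kaplan-Meier | time to death by nature | yes |
| Toxicities | graded events | no | no |

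Five of the six do not fit. Sections 3.1 and 6.3 give the later CTC draws as every 3 cycles rather than at cycle 4 only; either schedule is a sparse visit grid. Duration of response (Section 11) does not fill the gap, because its clock starts at response.

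**3. If PFS or follow-up time becomes the clock.** This was simulated. The inputs below are assumptions, except n:
- n = 28, standard-normal marker, two-sided 0.05;
- response 30% or 50%, independent of the marker;
- exponential follow-up time with mean 4·exp(−0.5x) months plus 0.1, where x is the marker value. This is a log hazard ratio of 0.5 per SD for progression, and exp(0.5) = 1.65.

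The Cox model takes this time as the clock and response as the event. The true marker-response association is zero.

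| Response rate | Cox, median log HR | Cox, false positives | Logistic, false positives |
|---|---|---|---|
| 30% | 0.51 | 21% | 3% |
| 50% | 0.53 | 36% | 4% |

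Across repeat runs the Cox figure lay between 19% and 36%. The median log HR of about 0.5 explains why: the model recovers the marker's effect on progression and labels it an effect on response. With no link between marker and progression, the same Cox model gave 4% to 5%.

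**4. If a proper time to response is built instead.** Response was placed on a 3-cycle visit grid and patients were censored at progression. The marker again acted on progression only (HR 1.65 per SD), with 6-month PFS of 10% or 30%. Cox gave about 1% to 5% false positives. A rank-sum test counting progressors as non-responders gave about 6% to 27%, depending on the assumed response and PFS rates. The choice of clock therefore matters, and so does the failure rule in any replacement.

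**5. Power.** With a true odds ratio of 2 per SD and n = 28, logistic regression has about 27% to 34% power.

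**The case against.** Much of the other side stands. PSA, pain and analgesic use are recorded on day 1 of every cycle (Section 8), so a time to response could be constructed. Censoring at progression then targets the cause-specific hazard of response, which is a legitimate quantity, and step 4 shows that such a model keeps its size when the marker acts on progression only.

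A reader might infer that Cox regression cannot give a valid association here, or that censoring progressors necessarily biases it. The documents do not support either reading. They contain no censoring rule to criticise, and a properly defined time-to-response analysis behaves acceptably. Nor do they say that PFS time would be the clock; step 3 shows what an unfilled gap permits, not what the plan prescribes.

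For RECIST response, the plan does have a failure rule: Section 10 (Reporting and Exclusions) counts progression, early death and unknown status as treatment failure. Applying it to the marker analysis is a reasonable choice of estimand, but it makes response a composite that a progression-only marker can also drive.

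Finally, the analysis is labelled hypothesis-generating and carries no decision rule. That limits the severity. It does not remove the mismatch, because a time to response could be defined but the plan does not define one.

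**Conclusion.** The stated method does not match most of the endpoints to which it is assigned. Cox regression suits PFS and OS; for the PSA, RECIST, pain, CTC and toxicity outcomes the plan supplies no event time or censoring rule and names no alternative. The mismatch is read directly from the documents and rests on no assumption.

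The size of the possible harm does rest on assumptions. About 19% to 36% false positives applies only if PFS or follow-up time is used as the clock and the marker affects progression at the assumed strength. Severity is minor: the analysis is exploratory, has low power under a standard logistic model at this sample size, and leaves the primary test (exact alpha 0.033, power 0.81) as it was.

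**What to change.** Amend the sentence in Section 10 and its copy in the Synopsis.

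- **PFS and OS:** Cox regression, as now.
- **PSA, RECIST, pain and CTC responses:** exact or Firth logistic regression on the baseline 20S level, or a rank-sum comparison with AUC, each with a 95% CI.
- **Denominators:** measurable disease at baseline for RECIST response; baseline PPI of at least 2 or analgesic need for pain response (Section 11); unfavorable baseline count for CTC conversion.
- **Failure rule:** for RECIST response, follow Section 10 (Reporting and Exclusions) and state that the result is a composite that a marker of progression alone can drive. Section 11 also limits evaluability to patients treated for one cycle and re-evaluated (or progressing earlier), which would drop some patients whom Section 10 counts as failures; say which rule governs here.
- **Toxicity:** occurrence of the event in treated patients, with no rule that turns stopping into non-response.

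If the sponsor prefers time to response, the plan should instead define its origin, event date, censoring, and the handling of progression and death as competing events.

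The cost is a wording change in two places and a small amount of extra programming. No new data, visits or patients are needed.
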